8.4 Method, Frequency, and Time Period for Detecting AEs and SAEs

Each subject will be monitored for AEs from the time of informed consent (Visit 1) through their last visit or follow up phone call. All AEs and SAEs, regardless of attribution (i.e., relationship to study drug), will be collected during this time period. The collection period

will end when the subject completes the Follow-Up phone call unless there is an ongoing AE which requires monitoring beyond this time point.

8.5 Documenting AEs and SAEs

All AEs that occur during the study should be documented in the subject's source documents in accordance with the investigator's normal clinical practice and in the AE section of the CRF.

The following information about each AE should be recorded in the source documentation and in the CRF:

- Dose of study drug
- Onset and cessation times
- Severity
- SAE (yes or no)
- Relationship to study drug
- Action taken in response to the event

Assessments of AE severity and of the possible relationship to study drug will be made by the investigator.

The investigator should attempt to establish a diagnosis of the event based on signs, symptoms, and other clinical information. Whenever possible, a diagnosis should be reported as the AE rather than just a sign or symptom. If a clinically significant abnormal laboratory finding meets the definition of an AE, a diagnosis or any clinical signs and symptoms rather than the abnormal laboratory finding should be recorded if possible. If no diagnosis is known and clinical signs and symptoms are not present, then the abnormal finding should be recorded as the AE.

8.6 Follow-Up of AEs and SAEs

All AEs must be followed until resolution, until the condition stabilizes, until the event is otherwise explained or is judged by the investigator to be no longer clinically significant, or until the subject is lost to follow-up. The investigator is responsible for ensuring that follow-up includes any supplemental investigations necessary to elucidate as completely as practical the nature and/or causality of the AE. This may include additional laboratory tests or investigations, histopathological examinations, or consultation with other health care professionals.

ZabBio, Inc. may request that the investigator perform or arrange for the conduct of supplemental measurements and/or evaluations of an AE. If a subject dies during participation in the study or during a recognized follow-up period, then ZabBio, Inc. should be provided with a copy of any post-mortem findings, including histopathology.

8.7 SAE Reporting

Any SAEs or Adverse Event of Interest should be reported within 24 hours of the investigator becoming aware of the occurrence, regardless of expectedness or causality. The investigator must call and then email the completed Serious Adverse Event Form to the contact information listed below.

The SAE form should be completed as thoroughly as possible and signed by the investigator or his/her designee before transmittal to the Sponsor/ZabBio, Inc.'s designee. It is **very important** that the investigator provide his/her assessment of causality to Study Treatment at the time of the initial SAE report.

Primary Medical Monitor:	[name]
	[contact]
[contact]
Alternate [contact]

SAE Reporting Contact Information

The Site Investigator will also forward an electronic copy of the SAE Report and supporting documentation (including discharge summaries progress notes, laboratory results) to the study team contacts via e-mail within 24 hours of receipt.

The site PI will perform a clinical review of the information provided to identify any missing data. The Site Investigator will also contact the study site to clarify any discrepant or missing information, to answer questions and to provide guidance to the site, if needed. The Investigator will be instructed to report the SAE as an acceptable medical diagnosis. If a preliminary diagnosis has not yet been made, then each symptom will be listed separately. A follow-up report will be issued when a diagnosis is made.

An updated SAE Report should be emailed within 48 hours of receipt of new or updated information. The investigator must also promptly notify the Institutional Review Board (IRB)/Independent Ethics Committee (IEC) of the occurrence of an SAE, including any follow-up information.

ZabBio, Inc. has a legal responsibility to notify regulatory authorities about the safety of a drug under clinical investigation. If a given SAE is considered related to the use of study medication and is unexpected, ZabBio, Inc. will forward a report of the event to the relevant regulatory health authority and to all investigators. It is the investigator's responsibility to promptly inform the IRB/IEC in accordance with local regulations.

An SAE that is considered related to study participation (e.g., as the result of any study procedures or invasive tests), even if it occurs during Screening or after the Follow-Up Visit, should be reported promptly to ZabBio, Inc.

8.8 **Post-Study AEs and SAEs**

Investigators are not obliged to actively seek AE information from former study participants. However, if the investigator learns of an SAE at any time after a subject has been discharged from the study and the event may reasonably be considered related to the use of study drug, the investigator should promptly telephone ZabBio, Inc.

8.9 Pregnancies

Participants are required to be protected from pregnancy by female surgical sterilization. However, should a pregnancy occur, it must be reported as soon as possible to the Sponsor or designee and recorded on the pregnancy CRF. The participant will be discontinued from the study and appropriate exit procedures will be followed. Note that pregnancy in itself is not regarded as an AE unless there is a suspicion that an investigational product may have interfered with the effectiveness of a contraceptive medication. If the participant has been exposed to study product, the course of the pregnancy should be followed until it has an outcome (spontaneous miscarriage, elective termination, normal birth or congenital abnormality). If the participant seeks care outside the site, every effort should be made to obtain her consent for the site to receive a copy of her medical records related to the pregnancy, its outcome and the health of the neonate, if applicable.

Reports of congenital abnormalities/birth defects are SAEs. Spontaneous miscarriages should also be reported and handled as SAEs. Elective abortions without complications should not be reported as AEs.

9 STUDY ADMINISTRATION

9.1 Safety monitoring

9.1.1 Protocol Safety Review Team (PSRT)

The study site investigators are responsible for continuous close safety monitoring of all study participants, and for alerting the Protocol Team and IRB if unexpected concerns arise. A subgroup of the Protocol Team, including the Medical Safety Officer, the Sponsor Project Physician, and the Site Investigator will serve as the Protocol Safety Review Team (PSRT). The PSRT and the study site will cooperate closely to monitor participant safety and respond to occurrences of toxicity in a timely manner. The following findings will serve as the minimum criteria to pause or stop enrollment in the study. However, the National Institutes of Health (NIH) and/or the PSRT can stop the study at any time for any concerning findings of lesser severity than those listed here:

- 1. If any participant manifests a grade 3 or higher AE that is judged to be related to study product.
- 2. If any participant develops deep epithelial disruption or ulceration of the genital epithelium.
- 3. If any participant develops erythema or edema of more than 50% of the combined vaginal and cervical surface (grade 2) or more than 50% of the vulvar surface (grade 2).

If enrollment is paused, its reinstitution will require the unanimous agreement of all members of the PSRT.

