6.5.2 Visit 2 (Enrollment)

- This visit will occur in the follicular phase of the menstrual cycle, preferably after menses ceases, on or before menstrual cycle day 10.
- Screening laboratory tests will be reviewed, along with the results of other inclusion and exclusion criteria, and eligible participants will be enrolled by entry into the Enrollment Log.
- She will be asked if there are any new or worsening medical problems or symptoms or used any medications since the last study visit. In addition, the participant will be asked if her male partner has had any adverse events (AEs) involving the urogenital system or whether he has had any serious AEs.
- She will be provided with an ovulation predictor kit (OPK) to help determine her midcycle point. Instructions for the proper use of the kit will be provided. Participants will be instructed to begin daily urine testing on day 10 of their cycle (adjusted as needed to their normal cycle length) and to contact the study coordinator if an OPK test is positive. Her mucus check visit will then be scheduled for the day of the positive test (preferred) or the next day at the latest. If the participant does not have a positive urine LH test by day 22, she will be considered anovulatory for this cycle.

- The participant will be instructed that from the start of her menses until 72 hours before her expected midcycle, she and her partner should use study-provided condoms for each act of intercourse. There should be no intercourse, use of intravaginal products (including spermicide) and her male partner should not have an ejaculation within 72 hours of expected mid-cycle date (visits 3, 6 and 9).
- 6.5.3 Visits 3, 6 and 9 (CMC Baseline [no product] Cycle, CMC ZB-06 Cycle, CMC postproduct-use safety Cycle)

This visit will be conducted on the day of ovulation or the day before or after, as determined by calculation or as identified by the presence of a positive test result with the OPK, whichever comes first.

- An interval history will be collected. Entry criteria will be reviewed to confirm the participant's eligibility.
- The participant will be asked if she has any new or worsening medical problems or symptoms or used any medications since the last study visit. In addition, she will be asked if her partner has had any AEs involving the urogenital system and whether he has had any serious AEs.

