- The participant will be asked whether she refrained from intercourse and the use of intravaginal products and whether her male partner refrained from ejaculation during the previous 72 hours. If instructions were not followed, she will be reinstructed. If she used a spermicide or spermicidally lubricated condom during the previous 72 hours, the visit will be rescheduled in the next cycle. Otherwise, the visit may continue at the investigator's discretion.
- Urine will be obtained for urinalysis and reflex urine culture at visits 3 and 6.
- A urine pregnancy test will be performed at visit 6
- A blood sample (approximately 3 teaspoons) will be obtained at visits 6 and 9. The participant will undergo a pelvic exam during which a sample of cervical and vaginal secretions will be examined for midcycle characteristics and the presence of sperm. At visits 3 and 6, a colposcopy exam of the cervix and vagina will be done to determine if there are signs of irritation of the external genitalia, cervix, and vagina, as observed with the naked eye will be noted.
- Vaginal pH will be determined at visits 3 and 6. A slide for Nugent score will be obtained at visit 6
- A speculum exam will be performed and vaginal swabs, aspirate, endocervical mucus and a cervicovaginal fluid lavage (CVL) will be obtained.
- If sperm are found in the vagina or cervical mucus, the baseline cycle will be rescheduled for the following month and instructions on the use of condoms and avoidance of ejaculation will be reviewed. Longer abstinence may be recommended

for couples that have reportedly complied with the required 72-hour period. Additional supplies will be provided as needed.

- If the cervical mucus score is <10, the participant may be asked to return in 1 or 2 days if it seems likely that the midcycle point has not yet been reached, or in the next cycle if it seems likely that the midcycle point has already passed.
- If no sperm are detected at this visit, and the cervical mucus score is ≥10, the participant will be instructed to return home and have intercourse without a condom 2 to 3 hours prior to Visits 4, 7 or 10, which will be scheduled for the same or following day, within 27 hours of the mucus check visit.

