9.1.2 Clinical Data Safety Review

The Data Management Team will generate data summaries for the PSRT after 8 couples have completed Study Visit 8. These data summaries will include adverse event, accrual and retention data. The Medical Safety Officer (or designee) will evaluate adverse event data independently and present those to the PSRT at this interim review, or at any time that significant safety concerns arise. The PSRT will determine whether or not the study protocol should continue as originally designed, should be changed, or should be terminated.

The IRB will be notified of any serious and unexpected adverse events according to the policies outlined in the EVMS IRB Policy and Manual of Operations.

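### The toxicity triggers in Section 9.1.1 pause enrollment (Visit 2) but do not by default hold dispensing or use of film (from Visit 6) in women already enrolled

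*Combined protocol and SAP*

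**What the plan says.** Section 9.1.1 (Protocol Safety Review Team) lists three findings: a product-related adverse event of grade 3 or higher; deep disruption or ulceration of the genital epithelium; and erythema or edema over more than half of the combined vaginal and cervical surface, or of the vulva. Their consequence is given as "The following findings will serve as the minimum criteria to pause or stop enrollment in the study". The restart rule reads "If enrollment is paused, its reinstitution will require the unanimous agreement of all members of the PSRT".

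The same section also gives wider powers. The NIH and/or the PSRT "can stop the study at any time for any concerning findings of lesser severity than those listed here", and it adds "The PSRT and the study site will cooperate closely to monitor participant safety and respond to occurrences of toxicity in a timely manner". Section 9.1.2 (Clinical Data Safety Review) provides for a review after 8 couples complete Visit 8, or whenever significant concerns arise: "The PSRT will determine whether or not the study protocol should continue as originally designed, should be changed, or should be terminated". Section 9.8 requires suspension or termination if the investigator or sponsor sees a serious medical risk.

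Enrollment is a defined act. At Visit 2 (Section 6.5.2), "eligible participants will be enrolled by entry into the Enrollment Log". The film is handed out at Visit 6, in the menstrual cycle after the baseline cycle (Sections 4.1, 5.5 and 6.5.3). At that visit, "Entry criteria will be reviewed to confirm the participant's eligibility"; if no sperm are seen and the mucus score is at least 10, the couple goes home to have intercourse before the postcoital visit, "which will be scheduled for the same or following day, within 27 hours of the mucus check visit". A back-up film may be given (6.5.3), and a failed product cycle may be repeated with a second film (4.2.4, 6.5.4).

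**The concern.** The purpose of a toxicity trigger is to interrupt exposure while someone decides what the finding means. In this design enrollment and exposure are separated by at least one no-product cycle, so a rule that acts on enrollment acts on the women furthest from the product. Two consequences follow from a literal reading. Pausing enrollment has no effect on any exposure due in about the first three weeks after a trigger, because the women it keeps out would not have reached the film by then. And once the last couple has been enrolled, the prescribed action has nothing left to act on, although women may still be waiting for film.

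This is the first use of the product in humans (Section 2.1.5), and Section 2.1.6 says that its risks are not known. What is at stake is a clear instruction to the staff dispensing at Visit 6. The primary comparison, its power and the safety analysis are untouched.

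**Working it through.** The plan gives no figure on this point, so there is none to reproduce. The check is a comparison of the texts, followed by a rough count for scale.

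**1. What each provision does to a woman who is enrolled but has not yet used the film**

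| Provision | Acts on | Automatic once a trigger occurs? |
|---|---|---|
| 9.1.1 triggers and restart rule | Enrollment (Visit 2) | These are the pre-specified criteria, but for enrollment only |
| 9.1.1 power of NIH/PSRT | Whole study | No; permissive |
| 9.1.2 PSRT determination | Whole protocol | No; a decision still to be made |
| 9.8 suspension | Whole study | No; rests on an opinion of serious risk |
| 4.2.3 withdrawal | One woman, on her own case | No; investigator's opinion |
| 6.5.3 conditions at Visit 6 | One couple: eligibility, abstinence, no sperm, mucus score | None asks whether a pause is in force |
| 5.5 drug accountability | Storage, dispensing log, returns | No hold mentioned |

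No provision makes a trigger hold dispensing, or use of a film already dispensed.

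**2. Time from enrollment to film**

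Lag from Visit 2 to Visit 6 = (cycle length − cycle day of Visit 2) + cycle day of Visit 6, with no repeat cycle. Cycle length is 21 to 35 days (4.2.1). Visit 2 is on or before day 10 (6.5.2); day 5 as the earliest is my assumption. Visit 6 is taken as day 10 to 22, the span of ovulation testing.

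- Short: (21 − 10) + 10 = 21 days = 3.0 weeks
- Middle: (28 − 7) + 14 = 35 days = 5.0 weeks
- Long: (35 − 5) + 22 = 52 days = 7.4 weeks

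Film use then follows within about a day of Visit 6.

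**3. Scale: women between Visit 2 and film at a given moment**

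Expected number = (couples enrolled ÷ accrual months) × (lag ÷ 30.44). The summary gives 15 evaluable women, up to 35 couples enrolled and 18 months in total. Individual participation is three months in the summary and 3 to 6 months in Section 4.1, which leaves 18 − 3 = 15 or 18 − 6 = 12 months of accrual. Even accrual is assumed.

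| Couples / months | Per month | Lag 21 d | Lag 35 d | Lag 52 d |
|---|---|---|---|---|
| 15 / 15 | 1.00 | 0.7 | 1.1 | 1.7 |
| 15 / 12 | 1.25 | 0.9 | 1.4 | 2.1 |
| 35 / 15 | 2.33 | 1.6 | 2.7 | 4.0 |
| 35 / 12 | 2.92 | 2.0 | 3.4 | 5.0 |

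So about one to five women. This is an illustration and bounds nothing. Repeated baseline cycles (4.1, Appendix B) lengthen the lag, and faster accrual raises the count in proportion. In the other direction, couples who leave during the baseline cycle never reach the film. The documents give no PSRT decision time, so the number who would fall due for film before a decision cannot be derived from them.

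**The case against.** The best case for the plan has three parts.

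- **The wording may mean more than it says.** Allowing the study to be stopped for findings less severe than those listed is a natural contrast only if the listed findings are already grounds for stopping the study. On that reading, enrollment is loose drafting. This stands as evidence of intent. It does not settle the text: both the trigger sentence and the restart sentence name enrollment, and enrollment has a fixed meaning at Visit 2. If a study stop was meant, adding a sentence simply makes the text say so.
- **Those who dispense are close to those who decide.** There is one site; its investigators must monitor safety continuously; and the Site Investigator sits on the PSRT. Dispensing in the face of a known trigger is unlikely. This stands, and it is the main reason why the practical risk is small.
- **Leaving holds to judgement is defensible** in a small study of a product planned as a single dose, with animal data that raise no significant concern. This stands in part. But the plan did choose to pre-specify triggers and a demanding restart rule, and it attached them to the step that does not expose anyone.

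A reader might infer that dosing could not be stopped after a trigger, or that the plan intends it to continue. The documents support neither: several parties may stop or suspend the study, and the PSRT and site are told to respond to toxicity promptly.

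**Conclusion.** The point holds as a gap in the default action. A trigger pauses enrollment under a pre-specified rule; whether enrolled women still receive or use film is left to a separate judgement. The lag of roughly 3 to 7 weeks between the two steps, without repeat cycles, is what makes the difference matter.

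The size is small. On even accrual over 12 to 15 months, a few women would be between Visit 2 and film use at any time, and they would be exposed only if a trigger occurred and staff went on dispensing, or an issued film was still used, before anyone intervened. A reader might want to turn this into a probability that a woman is dosed during a pause. The documents do not support one: they give no trigger rate, accrual pattern or PSRT decision time, and falling due for a film is not the same as being given it. Nothing in the efficacy or safety analysis changes. This is a worthwhile clarification for a first-in-human protocol and not a fatal defect.

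**What to change.** Add to Section 9.1.1 that any of the three triggers pauses both enrollment and all dispensing and use of ZB-06 film until the PSRT unanimously agrees to resume. Name what is covered: film due at Visit 6, back-up films, films for a repeated product cycle, and films dispensed but not yet used. The last item needs a line on how the site will reach the couple.

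Triggers 2 and 3 require neither exposure nor relatedness, and colposcopy is also done at the no-product Visits 3 to 5 (Appendix A), so a hold could follow a lesion in a woman who has never used the film. Add that the PSRT may release the hold, by the same unanimous vote, once it confirms that a trigger 2 or 3 finding arose in an unexposed woman. The trigger criteria themselves can stay as they are.

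The cost is a few sentences and, because film use is tied to midcycle, possibly one extra menstrual cycle for a couple caught in a hold, which departs from the consecutive-cycle sequence in Section 4.1. Sample size and power are unaffected.

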9.1.2 Clinical Data Safety Review

The Data Management Team will generate data summaries for the PSRT after 8 couples have completed Study Visit 8. These data summaries will include adverse event, accrual and retention data. The Medical Safety Officer (or designee) will evaluate adverse event data independently and present those to the PSRT at this interim review, or at any time that significant safety concerns arise. The PSRT will determine whether or not the study protocol should continue as originally designed, should be changed, or should be terminated.

The IRB will be notified of any serious and unexpected adverse events according to the policies outlined in the EVMS IRB Policy and Manual of Operations.

9.2 Data Handling and Recordkeeping

9.2.1 Study Data

Study data will be collected in an electronic database (Study-TRAX®) on direct web-portalentry CRFs, via a study laptop. The database will reside on servers at Biostatistics and Epidemiology Data Analytics Center (BEDAC) Boston University School of Public Health.

These eCRFs will serve as source data. Insler score data, and sperm motility and enumeration data from cervical mucus and vaginal pool samples will be initially recorded on a laboratory form, and transferred to a corresponding eCRF, but in this case, the laboratory form will serve as source data.

